8.4.3. Completion and transmission of SAE reports to GSK Biologicals

Once an investigator becomes aware that a SAE has occurred in a study subject, the investigator (or designate) must complete the information in the electronic Expedited Adverse Events Report **WITHIN 24 HOURS**. The report will always be completed as thoroughly as possible with all available details of the event. Even if the investigator does not have all information regarding a SAE, the report should still be completed within 24 hours. Once additional relevant information is received, the report should be updated **WITHIN 24 HOURS**.

The investigator will always provide an assessment of causality at the time of the initial report. The investigator will be required to confirm the review of the SAE causality by ticking the 'reviewed' box in the electronic Expedited Adverse Events Report within 72 hours of submission of the SAE.

8.4.3.1. Back-up system in case the electronic reporting system does not work

If the electronic reporting system does not work, the investigator (or designate) must complete, then date and sign a paper Expedited Adverse Events Report and fax it to the Study Contact for Reporting SAEs (refer to the [Sponsor Information](#)) or to GSK Biologicals Clinical Safety and Pharmacovigilance department within 24 hours.

This back-up system should only be used if the electronic reporting system is not working and NOT if the system is slow. As soon as the electronic reporting system is working again, the investigator (or designate) must complete the electronic Expedited Adverse Events Report within 24 hours. The final valid information for regulatory reporting will be the information reported through the electronic SAE reporting system.

8.4.4. Completion and transmission of pregnancy reports to GSK Biologicals

Once the investigator becomes aware that a subject is pregnant, the investigator (or designate) must complete the required information onto the electronic pregnancy report **WITHIN 2 WEEKS**.

Note: Conventionally, the estimated gestational age (EGA) of a pregnancy is dated from the first day of the last menstrual period (LMP) of the cycle in which a woman conceives. If the LMP is uncertain or unknown, dating of EGA and the estimated date of delivery (EDD) should be estimated by ultrasound examination and recorded in the pregnancy report.

8.4.5. Updating of SAE and pregnancy information after removal of write access to the subject's eCRF

When additional SAE or pregnancy information is received after removal of the write access to the subject's eCRF, new or updated information should be recorded on the appropriate paper report, with all changes signed and dated by the investigator. The updated report should be faxed to the Study Contact for Reporting SAEs (refer to the [Sponsor Information](#)) or to GSK Biologicals Clinical Safety and Pharmacovigilance department within the designated reporting time frames specified in [Table 15](#).

8.4.6. Regulatory reporting requirements for serious adverse events

The investigator will promptly report all SAEs to GSK in accordance with the procedures detailed in Section [8.4.1](#). GSK Biologicals has a legal responsibility to promptly notify, as appropriate, both the local regulatory authority and other regulatory agencies about the safety of a product under clinical investigation. Prompt notification of SAEs by the investigator to the Study Contact for Reporting SAEs is essential so that legal obligations and ethical responsibilities towards the safety of other subjects are met.

Investigator safety reports are prepared according to the current GSK policy and are forwarded to investigators as necessary. An investigator safety report is prepared for a SAE(s) that is both attributable to the investigational vaccine and unexpected. The purpose of the report is to fulfil specific regulatory and GCP requirements, regarding the product under investigation.

8.5. Follow-up of adverse events, serious adverse events, and pregnancies

8.5.1. Follow-up of adverse events and serious adverse events

8.5.1.1. Follow-up during the study

After the initial AE/SAE report, the investigator is required to proactively follow each subject and provide additional relevant information on the subject's condition to GSK Biologicals (within 24 hours for SAEs; refer to [Table 15](#)).

All SAEs documented at a previous visit/contact and designated as not recovered/not resolved or recovering/resolving will be reviewed at subsequent visits/contacts until the end of the study.

All AEs documented at a previous visit/contact and designated as not recovered/not resolved or recovering/resolving will be reviewed at subsequent visits/contacts until 30 days after the last vaccination.

8.5.1.2. Follow-up after the subject is discharged from the study

The investigator will follow subjects:

- with SAEs or subjects withdrawn from the study as a result of an AE, until the event has resolved, subsided, stabilised, disappeared, or until the event is otherwise explained, or the subject is lost to follow-up.
- with other non-serious AEs, until they are lost to follow-up.

If the investigator receives additional relevant information on a previously reported SAE, he/she will provide this information to GSK Biologicals using an electronic Expedited Adverse Events Report and/or pregnancy report as applicable.

GSK Biologicals may request that the investigator performs or arranges the conduct of additional clinical examinations/tests and/or evaluations to elucidate as fully as possible the nature and/or causality of the AE or SAE. The investigator is obliged to assist. If a subject dies during participation in the study or during a recognised follow-up period, GSK Biologicals will be provided with any available post-mortem findings, including histopathology.

8.5.2. Follow-up of pregnancies

Pregnant subjects will be followed to determine the outcome of the pregnancy. At the end of the pregnancy, whether full-term or premature, information on the status of the mother and child will be forwarded to GSK Biologicals electronic pregnancy report and the Expedited Adverse Events Report if applicable. Generally, the follow-up period doesn't need to be longer than six to eight weeks after the estimated date of delivery.

Regardless of the reporting period for SAEs for this study, if the pregnancy outcome is a SAE, it should always be reported as SAE.

8.6. Treatment of adverse events

Treatment of any AE is at the sole discretion of the investigator and according to current good medical practice. Any medication administered for the treatment of an AE should be recorded in the subject's eCRF (refer to Section 6.7).

8.7. Subject card

Study subjects' parent(s)/LAR(s) must be provided with the address and telephone number of the main contact for information about the clinical study.

The investigator (or designate) must therefore provide a “subject card” to each subject’s parent(s)/LAR(s). In an emergency situation this card serves to inform the responsible attending physician that the subject is in a clinical study and that relevant information may be obtained by contacting the investigator.

Subjects’ parent(s)/LAR(s) must be instructed to keep subject cards in their possession at all times.

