3. STUDY DESIGN OVERVIEW

N: Number of subjects planned to be enrolled

* Pre-vaccination: Blood sampling before the administration of the single HBV vaccine challenge dose

** Post-vaccination: Blood sampling one month after the administration of the single HBV vaccine challenge dose

Protocol waivers or exemptions are not allowed with the exception of immediate safety concerns. Therefore, adherence to the study design requirements, including those specified in the outline of study procedures (Section 5.5), are essential and required for study conduct.

- Experimental design: Phase IV, open-label, non-randomised, multi-centric, single-country study with a single group.
- Duration of the study: the intended duration of the study, per subject, will be approximately one month. The study will have a single epoch as follows:
 - Epoch 001: Primary starting at Visit 1 (Day 0) and ending at Visit 2 (Month 1).
- Study groups: the details are presented below in [Table 1](#).

Table 1 Study groups and epochs foreseen in the study

Study groups	Number of subjects	Age (Min/Max)	Epochs
			Epoch 001
HBV Group	300	14 years – 15 years	x

The treatment group details are provided in [Table 2](#).

Table 2 Study groups and treatment foreseen in the study

Treatment name	Vaccine name	HBV Group
Engerix-B Kinder	HBV	•

- Control: uncontrolled
- Vaccination schedule: A single dose of HBV vaccine will be administered to all subjects, who were previously primed and boosted with four doses of *Infanrix hexa* in the first two years of life.
- Treatment allocation: non-randomised
- Blinding: Refer to [Table 3](#).

Table 3 **Blinding of study epochs**

Study Epochs	Blinding
Epoch 001	open

- Sampling schedule: Blood samples will be taken from each subject at the following time-points:
 - Pre-vaccination: at Visit 1, before the administration of the single challenge dose of HBV vaccine.
 - Post-vaccination: at Visit 2, approximately one month after the single challenge dose of HBV vaccine.
- Type of study: self-contained
- Data collection: Electronic Case Report Form (eCRF).

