4.2. Inclusion criteria for enrolment

Deviations from inclusion criteria are not allowed because they can potentially jeopardize the scientific integrity of the study, regulatory acceptability or subject safety. Therefore, adherence to the criteria as specified in the protocol is essential.

All subjects must satisfy ALL the following criteria at study entry:

- Subjects' parent(s)/Legally Acceptable Representative(s) [LAR(s)] who, in the opinion of the investigator, can and will comply with the requirements of the protocol (e.g. completion of the diary cards, return for follow-up visits).
- Written informed consent obtained from the parent(s)/LAR(s) of the subject prior to performance of any study specific procedure.
- In addition to the informed consent that will be signed by the parents/LAR(s), written informed assent of the subject will be sought.
- A male or female between the ages of 14 to 15 (from and including the 14th birthday, up to but excluding the 16th birthday) at the time of vaccination.
- Healthy subjects as established by medical history and clinical examination before entering into the study.
- Subjects with documented evidence of previous vaccination with four consecutive doses of *Infanrix hexa* as part of routine vaccination in Germany: three doses of primary vaccination received by 9 months of age and one booster dose received between 11 and 18 months of age.
- Female subjects of non-childbearing potential may be enrolled in the study.
 - Non-childbearing potential is defined as pre-menarche, current tubal ligation, hysterectomy or ovariectomy.

Please refer to the [glossary of terms](#) for the definition of menarche.

- Female subjects of childbearing potential may be enrolled in the study, if the subject:
 - has practiced adequate contraception for 30 days prior to vaccination, and
 - has a negative pregnancy test on the day of vaccination, and
 - has agreed to continue adequate contraception during the entire treatment period and for 2 months after completion of the vaccination series.

Please refer to the [glossary of terms](#) for the definition of adequate contraception.

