5.6.10. Study Vaccine administration

- After completing all prerequisite procedures prior to vaccination, one dose of study vaccine will be administered intramuscularly (IM) in the deltoid region of the non-dominant arm (refer to Section 6.3 for detailed description of the vaccine administration procedure). If the investigator or delegate determines that the subject's health on the day of administration temporarily precludes vaccine administration, the visit will be rescheduled within the allowed interval for this visit (see [Table 5](#))
- The subjects will be observed closely for at least 30 minutes following the administration of the vaccine, with appropriate medical treatment readily available in case of anaphylaxis.

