5.6.12. Recording of AEs, SAEs and pregnancies

- Refer to Section 8.3 for procedures for the investigator to record AEs, SAEs and pregnancies. Refer to Section 8.4 for guidelines and how to report SAE and pregnancy reports to GSK Biologicals.
- The subjects' parent(s)/LAR(s) will be instructed to contact the investigator immediately should the subjects manifest any signs or symptoms they perceive as serious.
- At the vaccination visit (Visit 1), diary cards will be provided to the subject's parent(s)/LAR(s). The subject's parent(s)/LAR(s) will record body (axillary) temperature and any solicited local/general AEs (i.e. on the day of vaccination and during the next 3 days) or any unsolicited AEs (i.e. on the day of vaccination and during the next 30 occurring after vaccination. The subject's parent(s)/LAR(s) will be instructed to return the completed diary card to the investigator at the next study visit.

Note: Diary cards can be filled in by a minor subject under the supervision of the subject's parent(s)/LAR(s) provided that the minor has the competency to assess and report the information to be provided in the diary card. The ultimate accountability for the completion of the diary cards remains with the subject's parent(s)/LAR(s).

The investigator should discuss this accountability with the subject's parent(s)/LAR(s).

- Collect and verify completed diary cards during discussion with the subject's parent(s)/LAR(s) on Visit 2.

Note: If the diary card has been filled in by a minor subject, the investigator or delegate should verify the reported information during a discussion with the minor subject preferably in the presence of his/her parent(s)/LAR(s).

- Any unreturned diary cards will be sought from the subject's parent(s)/LAR(s) through telephone call(s) or any other convenient procedure. The investigator will transcribe the collected information into the eCRF in English.

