5.3. Important protocol deviation not leading to elimination from ATP cohort

The following important protocol deviations will be reported:

- In case of unexpected vaccinations at study start was granted due to regulatory recommendation, the subjects who had such vaccination could be mentioned.
- Subjects attending visit 2 alone without parents being present.
- Protocol deviations related to informed consent and not leading to eliminations.

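### Protocol Section 8.7 gives the subject card only to the parents, so it may be missing when a 14-15-year-old needs emergency care without a parent present

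*Protocol*

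**What the plan says.** Protocol Section 8.7 first requires that the parents or legal representatives receive the address and telephone number of the main study contact, and makes this the reason for issuing a card to them. It then adds a second function: "In an emergency situation this card serves to inform the responsible attending physician that the subject is in a clinical study", with the investigator as the source of further information. The section ends by stating that the parents "must be instructed to keep subject cards in their possession at all times".

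Eligible subjects are aged 14 to 15, defined in Protocol Section 4.2 as "from and including the 14th birthday, up to but excluding the 16th birthday". On time in the trial, Protocol Section 3 states that "the intended duration of the study, per subject, will be approximately one month".

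No other section of the protocol or SAP gives a card, or a copy of one, to the subject. Neither document forbids it.

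**The concern.** The emergency function depends on the card being where the patient is. For an infant, a card kept by a parent is almost always with the patient. For an adolescent it need not be. If a subject is taken ill at school and a physician treats the subject before a parent arrives, a card held as Section 8.7 instructs is somewhere else.

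At stake is the prompt that leads an outside physician to contact the investigator. Without it, that physician may not learn at the time that the subject received a study vaccine within the past month, and the site may hear of the event later than it could have. This concerns subject safety and the speed of reporting. It does not bear on the estimate of any immunogenicity or reactogenicity endpoint.

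**Working it through.** The point is textual. It depends on no rate, power or sample-size figure, and the plan states no figure that could be reproduced. The check sets the relevant sections side by side.

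1. **Who holds the card.** In the last sentence of Protocol Section 8.7 the parents or legal representatives are the grammatical subject, so the possession referred to is theirs. The preceding sentence also names them as the recipients. Followed to the letter, a single card stays with the parent.

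2. **What the card is for.** Section 8.7 gives two functions. For the contact details, the parents are the right holders. For the emergency function ("In an emergency situation this card serves to inform the responsible attending physician that the subject is in a clinical study"), the person who needs to see the card is the physician beside the subject.

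3. **Whether subject and parent can be apart.** Protocol Section 8.3.3.2.1 illustrates a grade 3 adverse event in adolescents as one that would stop them going to school. The plan therefore takes school attendance as normal. SAP Section 5.3 lists "Subjects attending visit 2 alone without parents being present" among the important deviations to be reported. That shows unaccompanied attendance was thought possible. It is classed as a departure from plan, relates to a scheduled visit and carries no frequency, so it is weaker evidence than the school example.

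4. **Whether the protocol adapts to adolescents elsewhere.** It does. Section 5.1 requires written assent from each capable subject. Section 5.6.12 allows the subject a part in safety reporting: "Diary cards can be filled in by a minor subject under the supervision of" the parents or legal representatives. Section 8.7 gives the subject no comparable part.

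5. **What else covers the same ground.**
   - *Capture of serious adverse events.* Sections 5.6.12 and 8 tell parents to contact the investigator at once about anything they perceive as serious. Under Section 5.6.12 diary cards cover Day 0 to Day 30, are verified at Visit 2, and are chased if not returned. Section 8.3.3.1 adds active questioning. Section 8.3.3.4 asks about hospitalisation and emergency room visits for every symptom.
   - *Acute risks.* Section 1.3.1 pairs hypersensitivity with post-vaccination observation, and Section 5.6.10 repeats that subjects are "observed closely for at least 30 minutes following the administration of the vaccine". Syncope is handled by procedures against injury from falls (Sections 1.3.1 and 6.6).
   - *Blinding.* The study is open-label with one dose of a commercial vaccine (Sections 5.3 and 6.1), so a treating physician has no blind to break.

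Steps 1 to 3 establish the mismatch: the holder suits one function of the card and fits the other poorly. Step 5 limits what follows from it.

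**The case against.** The strongest reply is that Section 8.7 is sound for the purpose it states first. The parents need the study contact details and should hold the card. A parent who is present, or who can be reached by telephone, can pass those details to a physician. Nothing stops a site from giving the subject a copy. All of this stands, and it is why the parents should keep a card under any amendment. It does not meet the case in which no parent is at hand. That a second card is permitted does not mean that one is provided.

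Three stronger readings are tempting, and the documents support none of them.

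- *A reader might infer that the card cannot do its job.* It does so whenever a parent is present or reachable.
- *A reader might infer that detection of serious adverse events depends on the card.* The routes listed above operate without it. A report could be delayed, but it would not necessarily be lost. The card is also not the named mitigation for hypersensitivity or syncope.
- *A reader might try to size the problem by hours away from home.* If one assumes 6 to 8 hours on each of five weekdays, the card is absent for 6 × 5 = 30 to 8 × 5 = 40 of 168 hours a week, or 30/168 = 17.9% to 40/168 = 23.8%. The arithmetic is right, but the hours are assumed and appear in neither document. The result measures time without a card. It does not measure emergencies in which the card would have changed care or reporting.

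**Conclusion.** The concern holds as a minor mismatch between a stated rule and one of its two stated functions. As Section 8.7 is written, the card may be unavailable to the physician when a subject aged 14-15 needs emergency care without a parent present.

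The safety gain from correcting this is modest. Follow-up lasts about a month after a single dose, the acute risks have separate precautions, and several other routes bring serious events to the investigator. No endpoint, analysis cohort, sample size or analysis changes. The number of emergencies affected cannot be estimated from the documents and may be very small.

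The conclusion assumes that sites follow Section 8.7 literally and issue one card per family. The Study Procedures Manual is not among the documents reviewed and might provide for a second card. Protocol Section 5.4, however, describes that manual as holding information without impact on subject safety, so it is not the natural place for such a rule.

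**What to change.** Amend Protocol Section 8.7 so that the investigator (or designate) gives one subject card to the subject, to be carried throughout the study, and a copy to the parents or legal representatives, who keep it for the study contact details. The instruction on possession should then name both holders.

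The cost is one more card for each of the approximately 300 planned subjects, so about 300 more printed cards, and a short change to the text. No visit, procedure, staff time of note or change to the SAP is needed.

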9. SUBJECT COMPLETION AND WITHDRAWAL

9.1. Subject completion

A subject who returns for the concluding visit foreseen in the protocol is considered to have completed the study.

9.2. Subject withdrawal

Withdrawals will not be replaced.

9.2.1. Subject withdrawal from the study

From an analyses perspective, a ‘withdrawal’ from the study refers to any subject who did not come back for the concluding visit foreseen in the protocol.

All data collected until the date of withdrawal/last contact of the subject will be used for the analyses.

A subject is considered a ‘withdrawal’ from the study when no study procedure has occurred, no follow-up has been performed and no further information has been collected for this subject from the date of withdrawal/last contact.

Investigators will make an attempt to contact those subject’s parent(s)/LAR(s) who do not return for scheduled visits or follow-up.

Information relative to the withdrawal will be documented in the eCRF. The investigator will document whether the decision to withdraw a subject from the study was made by the subject’s parent(s)/LAR(s), or by the investigator, as well as which of the following possible reasons was responsible for withdrawal:

- Serious adverse event.
- Non-serious adverse event.
- Protocol violation (specify).
- Consent withdrawal, not due to an adverse event*.
- Moved from the study area.
- Lost to follow-up.

- Other (specify).

*In case a subject is withdrawn from the study because the subject's parent(s)/LAR(s) has withdrawn consent, the investigator will document the reason for withdrawal of consent, if specified by the subject's parent(s)/LAR(s), in the eCRF.

Subjects who are withdrawn from the study because of SAEs/AEs must be clearly distinguished from subjects who are withdrawn for other reasons. Investigators will follow subjects who are withdrawn from the study as result of a SAE/AE until resolution of the event (see Section 8.5.1.2).

